7.3 Clinical data

To date, no clinical trials of [¹⁸F]CETO have been performed in humans. We are therefore seeking the necessary approvals to allow us to undertake a First-in-Human (FiH) trial. We propose to study up to five healthy volunteers and six patients with confirmed PA to assess the safety and tolerability of [¹⁸F]CETO. These studies will also provide an early indication of the extent of uptake of [¹⁸F]CETO by both normal and abnormal human adrenal glands. Healthy volunteers will receive a single dose of the tracer followed by a PET-CT scan. Six patients with PA (three with unilateral PA and three with bilateral PA) will each receive [¹⁸F]CETO followed by a PET-CT scan on up to two occasions to allow us to determine whether pre-treatment with a short (72 hour) course of dexamethasone can improve the signal to background uptake of [¹⁸F]CETO, as we have previously demonstrated for 11C-Metomidate¹.

8 Rationale for Trial

AVS is currently the gold standard for lateralisation in PA. However, it has several limitations, including technical failures and a need to discontinue confounding medications that may interfere with interpretation. These severely limit its availability and utility in routine clinical practice. Our solution to address this has been to use PET coupled with the radiopharmaceutical [11C]metomidate ([11 C]MTO) for molecular adrenal imaging. However, [11 C]MTO is limited by a short half-life ($t_{1/2}$ = 20 minutes) therefore restricting this imaging modality to facilities with an on-site cyclotron. [18 F]CETO has a longer half-life ($t_{1/2}$ = 110 minutes). It can be distributed to centres 100-150 miles from the primary radiopharmacy site. Preclinical studies have suggested a higher adrenal selectivity with reduced uptake by adjacent organs (e.g. liver, spleen) in comparison to [11 C]MTO. Therefore, we anticipate [18 F]CETO will offer increased

efficacy in PA lateralisation in addition to promoting the creation of a national network for molecular imaging in PA.

The expected dose of [¹⁸F]CETO is in the range of 0.2μg to 2μg which is based on data from a validated production method as described in the investigational medicinal product (IMP) dossier. The selected dose is close to the maximum allowed, estimated from dosimetry calculations and taking into account animal *in vivo* studies. Based on clinical data derived from this study, we will be able to predict what dose should be sufficient to give the required signal to noise ratio, and to be used in future studies. The administration of up to 10μg of the study drug is regarded as safe due to [¹⁸F]CETO being a very close analogue to the well-known registered drug Etomidate. The total radiation dose to patients participating in two [¹⁸F]CETO PET-CT scans is below 10mSv which is the current standard limit for healthy controls in clinical PET research studies⁸. There is no anticipated clinical benefit for participants in this study. This is a Proof-of-Concept study to investigate the safety and efficacy of [¹⁸F]CETO.

9 Trial Design

9.1 Statement of Design

This is a Phase 1, single-centre, open label, micro-dosing study.

9.2 Number of Centres

This is a single-centre study conducted at Cambridge University Hospitals NHS Foundation Trust.

9.3 Number of Participants

We intend to recruit 11 participants: 5 of these subjects will be healthy controls, and 6 will be patients with PA (three with unilateral disease and three with bilateral disease as lateralised on prior AVS). Recruitment of healthy volunteers and patients will occur concurrently (i.e. it will not be necessary for all healthy volunteers to be recruited before patients will be recruited).

9.4 Participants Trial Duration

The trial duration will be approximately 1 month and will consist of:

- A screening visit (1-2 hours duration) conducted up to 28 days prior to the scan
- A baseline visit (lasting up to 2 hours) prior to the PET-CT scan
- Injection of [¹⁸F]CETO followed by a 90 minute PET-CT scan for both healthy volunteers and patients
- All participants will remain in the PET-CT unit for up to 4 hours, following which they
 will be admitted to the clinical research facility (CLRF) for approximately 24 hours
- Where required, a 7 (+/- 2) day follow up visit (lasting up to 2 hours) for repeat synacthen testing
- Patient self-administration of Dexamethasone for 3 days
- Patients (but not healthy volunteers) will attend for a repeat administration of [18F]CETO followed by a 90 minute PET-CT scan ≥7 days following the initial scan. On this occasion, they will be discharged following a 4 hour observation period on the PET-CT unit. There will be no requirement for patients to have an overnight

observation period on the CLRF following the repeat PET-CT scan due to tolerance of [18F]CETO administration and normal blood results following the initial PET-CT scan.

9.5 Trial Objectives

9.5.1 Primary objective

• To evaluate the safety of up to two administrations of [¹⁸F]CETO in up to 6 patients with primary aldosteronism and 5 healthy volunteers.

9.5.2 Secondary objectives

- To assess [18F]CETO uptake by the adrenal glands
- To evaluate uptake in bilateral vs unilateral cases of PA following [18F]CETO administration in up to 6 patients

9.6 Trial Outcome Measures

9.6.1 Primary outcome Measure

• The primary outcome measure is the overall safety of [¹⁸F]CETO. This will be assessed according to the frequency of adverse events, serious adverse events, clinically significant changes in vital signs, ECG and laboratory parameters.

9.6.2 Secondary outcome measures

- [18F]CETO uptake by the adrenal glands will be assessed by measurement of Standardized Uptake Values (SUV) over the left and right adrenal glands: all assessments will be performed by a dedicated blinded reviewer.
- Evaluation of adrenal uptake of [¹⁸F]CETO in bilateral versus unilateral cases of PA will be performed by comparing SUV values of both adrenal glands in three patients with each subtype of PA (using a dedicated blinded reviewer).

10 Selection and withdrawal of participants

10.1 Inclusion Criteria

Inclusion Criteria:

Healthy Volunteers

To be included in the trial the participant must:

- give written informed consent
- be aged 50 years or over
- have no underlying medical conditions
- be able to lie down for at least 2 hours and not be claustrophobic

In addition, all female participants must be:

• post-menopausal (no menses for 12 months, without an alternative medical cause)

Patients

To be included in the trial the patient must:

- give written informed consent
- be aged 40 years or over

- be able to lie down for at least 2 hours and not be claustrophobic
- fulfil the following criteria:
 - have a confirmed diagnosis of PA as per Endocrine Society guidelines
 - At least one paired measurement of plasma renin and aldosterone, measured off Spironolactone/Eplerenone within past 12 months, showing ARR above local threshold value.
 - One of the following two criteria:
 - Plasma aldosterone>190pmol/L following saline infusion.
 - Spontaneous hypokalaemia, suppressed plasma renin and plasma aldosterone>550pmol/L.
 - have undergone successful lateralisation of the cause of PA to one or both adrenal glands by adrenal vein sampling (AVS).
 - be willing to have two scans

In addition, all female patients must have a negative (blood) pregnancy test at the screening visit.

10.2 Exclusion Criteria

All participants:

- allergy to radiographic contrast agents
- allergy or contraindication to synacthen
- pregnancy, breastfeeding, or the intention to become pregnant during the 6 months following trial participation
- positive pregnancy test at the screening or baseline visits
- assessed by the investigator as being unable or unwilling to comply with the requirements of the study protocol.
- receipt of another IMP as part of a CTIMP
- prior radiation exposure as part of previous research studies
- recreational drug use, or substance/alcohol dependency
- clinically abnormal screening blood tests [including abnormal short synacthen test (SST)].

Additional exclusion criteria for **healthy volunteers**:

- women of child-bearing potential (i.e. fertile, following menarche and until becoming post-menopausal unless permanently sterile. Permanent sterilisation methods include hysterectomy, bilateral salpingectomy and bilateral oophorectomy)
- exposure to radiation during their work
- received more than 10 mSv of radioactivity in the past 12 months
- any subject with a history of adrenal disease or who, at the screening visit, reports symptoms, or exhibits physical signs, that could be consistent with previously unsuspected adrenal disease

Additional exclusion criteria for **patients**:

• allergy or contraindication to dexamethasone treatment (or lactose intolerant)

10.3 Participant Withdrawal Criteria

A participant can decide to withdraw from the trial at any time without further explanation. Participants may be removed from the trial at their choice or at Investigator's discretion if it is felt to be clinically appropriate. Reasons for participant withdrawal will be recorded in the Case report form (CRF). The participant will be reassured that their future care will not be affected by their withdrawal, and that their relationship with their responsible physician remains unaltered. The participant will be informed that any of their study data already stored will be retained, and will be used, if necessary, in the evaluation of the study drugs and for adherence to the relevant regulatory requirements.

Any participants who have their dosing discontinued will be withdrawn from the trial (as described in Section 11.5 Ongoing Safety Review). Withdrawal from the trial will also occur in the event of participant pregnancy. Healthy volunteers will be withdrawn from the trial in the event that they are taking medication at the point of [18F]CETO administration.

11 Trial Treatments

For the purpose of this trial, the radiopharmaceutical [¹⁸F]CETO, administered intravenously, is considered a Investigational Medicinal Product (IMP).

Oral dexamethasone is considered as a Non- Investigational Medicinal Product (nIMP) within this trial and will be supplied by local site's own stock, using standard labels and packaging.

The investigator is responsible for ensuring that deliveries of [¹⁸F]CETO and other study materials are safely and properly received, recorded, handled, and stored in accordance with all applicable regulatory guidelines, and used in accordance with this protocol. This responsibility may be delegated to appropriately trained personnel.

11.1 Treatment Summary

[¹⁸F]CETO injection is a radiopharmaceutical, and will be handled in accordance with all applicable regulations. Radiopharmaceuticals will be used only by personnel (e.g radiopharmacists, radiographers) who are qualified by specific training in safe use and handling of radioactive drugs and materials. Also, care will be taken to ensure minimum radiation exposure to the patient and all personnel involved in the procedure.

The IMP consists of the radiopharmaceutical [18 F]CETO. The manufacture of [18 F]CETO will be performed at the Wolfson Brain Imaging Centre (WBIC) Radiopharmaceutical Unit in Cambridge, UK. Details of manufacture of [18 F]CETO for injection are outlined in the IMPD. Due to being radiolabelled with a short-lived radioisotope (fluorine-18 $t_{1/2}$ = 110 minutes) the IMP is produced "on demand" for which stability studies have established a shelf life of 8 hours. No long-term storage is required.

A batch release certificate of the product is provided by the Qualified Person (QP) of the manufacturing site to the investigational centres to confirm that the product is suitable for administration, and that it meets the drug product specifications stated in the Investigational Medicinal Product Dossier (IMPD), including the filter integrity test requirements.

A summary of the IMP components is given below

Chemical name: 2-[18F]fluoroethyl1-[(1R)-1-(4-chlorophenyl)ethyl]-1H-imidazole-5-

carboxylate

Formulation: 15.2 mL phosphate buffer pH 7.4, 0.8 mL EtOH, 0.9% Sodium

Chloride Injection

Manufacturer: Radiopharmaceutical Unit, Wolfson Brain Imaging Centre,

[name]

Storage: At room temperature, Shelf life of 8 hours

11.1.1 Name and description of IMP [18F]CETO

11.1.1.1 Legal status

The trial is being carried out under a Clinical Trial Authorisation. The drug is therefore only to be used by the named investigators, for the participants specified in this protocol, and within the trial.

11.1.1.2 Supply

For the trial studies at Cambridge University Hospitals NHS Foundation Trust (CUH) PET-CT Unit, the [¹8F]CETO will be supplied as a sterile solution in multidose vials by the nearby WBIC Radiopharmaceutical Unit (University of Cambridge), where it will be manufactured, packaged and labelled at a qualified and GMP-validated facility. The product will be delivered using "Type A" radioactivity containers to reduce any radioactivity exposure to the operators. Supply will be initiated on receipt of a suitably signed radiopharmaceutical prescription form as part of the manufacturing standard operating procedures.

Before administration, the suitability of each preparation will be assessed for radioactivity, as well as by high-performance liquid chromatography (HPLC) and pH measurement. Suitable preparations will be certified by a QP according to approved standard operating procedures (SOPs) of the GMP manufacturing site.

11.1.1.3 Packing and Labelling

Labels will be prepared in accordance with Good Manufacturing Practice Annex 13 requirements and local regulatory guidelines.

[¹⁸F]CETO will only be dispatched to site after receipt of confirmation that the regulatory checklist is complete. Due to the short half-life of [¹⁸F]CETO orders will be made on a per-patient basis. For each injection, a release certificate will be provided by email which will include the following information: batch number, date of preparation, radioactive concentration of injection (MBq/ml) at stated time and shelf life.

11.1.1.4 Storage conditions

EudraCT Number: 2018-004851-18

[¹⁸F]CETO must be stored in a secure area with access limited to authorised site staff only. [¹⁸F]CETO Injection should be stored at room temperature in a lead-shielded container and in accordance with national regulations for radioactive materials. The precautions normally taken when handling radioactive materials will be observed. Maintenance of a temperature log (manual or automated) is required. For further information investigators should refer to the investigator brochure and IMP Handling Manual.

11.1.1.5 Maximum duration of treatment of a participant

Healthy volunteers will be given a single dose of [18F]CETO only.

Patients will have administration of up to two [18F]CETO doses across two separate visits.

11.1.1.6 Radiation Exposure

The administered activity of [¹⁸F]CETO will be at a dose of 2 Mega-Becquerel (MBq)/kg, up to a maximum of 200MBq (based on a 100kg patient). The activity concentration of 2MBq/kg has been identified on pre-clinical animal data to show good adrenal uptake. The administered radioactivity of [¹⁸F]CETO will be recorded on the PET treatment record, and should be within +/-10% of the prescribed activity based on weight. No dose escalation will be performed in the trial; however, dose optimisation will be performed on conclusion of the study for guiding optimal dose in future studies.

		Maximum Effective dose (mSv)	
		Healthy Volunteers	Patients
Initial PET- CT Scan	PET	4.10	4.10
	Low dose CT	0.81	0.81
Repeat PET- CT Scan (Patients only)	Second PET	n/a	4.10
	Second low dose CT	n/a	0.81
	Total dose	4.91	9.82

Abbreviations: n/a not applicable

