Procedures: Screening & enrolment	 Medical history (including medications) and physical examination 12-Lead ECG Pregnancy test (serum hCG) in females of child-bearing potential Blood tests: - full blood count (FBC) (haemoglobin, white cell count, platelet count) - urea & electrolytes including creatinine (U&Es), bicarbonate - liver function (LFTs) [bilirubin, alanine transaminase (ALT), alkaline phosphatase (ALP)] -short synacthen test (SST) Urine tests: - drugs of abuse screen (amphetamine, cocaine, marijuana, benzodiazepine, tricyclic antidepressant, barbiturates, metamphetamine, morphine, methadone, MDMA) Inclusion/exclusion criteria review
Procedures: Baseline	 Confirmation of continued willingness and eligibility to participate in the study Update to medical history (including current medication) and physical examination Recording of participant demographics Repeat 12-lead ECG Pregnancy test (urine hCG) in females of child-bearing potential Blood tests: FBC U&Es, bicarbonate LFTs Direct Renin Concentration (DRC) Plasma Aldosterone Concentration (PAC) Adrenocorticotropic Hormone (ACTH)
Procedures: Treatment period	Each participant will receive 100-200 MBq [18F]CETO by intravenous injection. Following diagnostic and attenuation correction CT, dynamic PET image acquisition will be performed for 90 minutes. Following completion of the PET-CT scan, both patients and healthy volunteers will be

admitted for an approximately 24-hour observation period on the Clinical Research Facility (CLRF).

On the morning following the scan, blood samples will be taken which will include the following:

- FBC
- U&Es
- LFTs
- Short Synacthen Test

Patient-specific Activities (for patients who returned normal SST results)

Patients will be provided with a prescription for dexamethasone 500 micrograms to be taken four times daily for three days (total 12 doses). Dexamethasone will be selfadministered for three days prior to the repeat PET-CT scan. Patients will be provided with contact details for the research team if they have questions while taking any dexamethasone.

Patients will undergo a repeat scan ≥7 days after the first PET-CT scan following dexamethasone pre-treatment as part of standard clinical care.

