12.5 Trial assessments

IMP Administration & PET-CT

Healthy volunteers and patients will attend the PET-CT unit at CUH. Recruitment of healthy volunteers and patients will occur concurrently (i.e. it will not be necessary for all healthy volunteers to be recruited before patients will be recruited). All scans will be performed on a GE Discovery PET-CT scanner. During the [¹⁸F]CETO injection and the PET-CT scan, a clinical research fellow and research nurse will supervise the participant. We will perform sentinel dosing for the first overall IMP dose on the trial. Specifically, only a single participant will receive the IMP and proceed through the trial before any subsequent participants are administered with the IMP. The Principal Investigator will be present during the first injection of [¹⁸F]CETO in the first participant. For subsequent injections, the Principal Investigator will be contactable by the unit in the unlikely event of an emergency. Details of the emergency equipment and processes for the PET-CT Unit can be found in section 13 Toxicity - Emergency Procedures.

A detailed description of the IMP administration and PET-CT scan process is described below:

- Participants will be asked to void their bladder before the PET-CT scan
- A positioning attenuation correction (CTAC) scan will be performed.
- Participants will then receive a 2MBq/kg IV injection of [¹⁸F]CETO, up to a maximum of 200 MBq. The radiotracer will be injected over approximately 30 seconds.
- A dynamic PET scan will occur immediately following the injection of [¹⁸F]CETO and will last for 90 minutes from the point of injection. Dynamic scanning will be performed to provide information on the optimum image acquisition window.
- List-mode PET data acquisition will last for the duration of imaging and facilitate the creation of retrospective static and dynamic images needed for optimisation.
- Pulse oximetry will be acquired and recorded throughout imaging.
- At the end of the scan participants will be asked to void their bladder and drink water ad libitum as this promotes the removal of radioactive material from the body
- Vital signs will be measured, and a 12-lead ECG will be performed after the scan

In the unlikely event of a failure of tracer production (with no ability to rectify on the day in question), participants will be rescheduled for a PET-CT scan on a separate date.

Period of Observation

Following the IMP administration and PET-CT scan, the following will occur:

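### The 200 MBq maximum and the +/-10% activity tolerance conflict above about 182 MBq, and the 9.82 mSv two-scan maximum states neither the activity behind it nor clearly which CTs it counts

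*Protocol*

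**What the plan says.** Section 11.1.1.6 sets the administered activity at 2 MBq/kg, "up to a maximum of 200MBq (based on a 100kg patient". The same paragraph says that the recorded administered radioactivity "should be within +/-10% of the prescribed activity based on weight". It does not say whether the upper side of that tolerance stops at 200 MBq. Section 12.5 repeats the 2 MBq/kg rule and the 200 MBq maximum without mentioning the tolerance. The synopsis also gives 200 MBq as the upper end of what participants receive.

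The table in section 11.1.1.6 is headed "Maximum Effective dose (mSv". Per scan it lists 4.10 mSv for PET, and for CT "Low dose CT 0.81 0.81" (healthy volunteers, then patients). Its last row reads "Total dose 4.91 9.82". The activity to which 4.10 mSv belongs is not given.

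Section 8 says that the total for patients having two scans "is below 10mSv which is the current standard limit for healthy controls in clinical PET research studies".

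On CT, the synopsis (treatment period) says "Following diagnostic and attenuation correction CT, dynamic PET image acquisition will be performed for 90 minutes", whereas the step-by-step procedure in section 12.5 says only "A positioning attenuation correction (CTAC) scan will be performed".

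**The concern.** A table of maximum doses should hold for every administration that the protocol accepts. Here one paragraph contains both a ceiling on activity and a tolerance that, at the upper end of the weight range, extends past that ceiling. The protocol's own reference patient of 100 kg lies in the range where the two rules disagree. Because the two-scan total is within 0.18 mSv of the quoted 10 mSv, the reading chosen decides whether the statement in section 8 is true.

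The CT wording raises the same question by another route. If the synopsis describes a CT that the table leaves out, the total is incomplete whatever is decided about activity.

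At stake is the accuracy of a safety figure in a first-in-human study whose participants are told to expect no clinical benefit, and whether site staff can tell which delivered activities are within protocol.

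**Working it through.** **Inputs.** PET 4.10 mSv and CT 0.81 mSv per scan; 2 MBq/kg; maximum 200 MBq; tolerance +/-10% (all section 11.1.1.6). Up to two scans for patients and one for volunteers (section 11.1.1.5). Comparison value 10 mSv (section 8).

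**1. The protocol's own figures.** One scan: 4.10 + 0.81 = 4.91 mSv. Two scans: 2 x 4.91 = 9.82 mSv. Both reproduce.

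**2. Where the two rules collide.** A prescription P delivered at +10% exceeds 200 MBq when 1.10 x P > 200, that is P > 181.8 MBq. At 2 MBq/kg this is a weight above 90.9 kg. For example, a 95 kg patient is prescribed 190 MBq; the tolerance accepts up to 209 MBq; the maximum does not. This conflict needs no assumption about dosimetry.

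**3. Room below 10 mSv.** 10 - 9.82 = 0.18 mSv over two scans, or 0.09 mSv per scan. As a share of the PET dose: 0.18 / 8.20 = 2.2%.

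**4. Conditional upper case.** Two assumptions that the protocol does not state: 4.10 mSv is the dose at 200 MBq, and the tolerance may go above 200 MBq. PET dose is scaled in proportion to activity.
- Dose per unit activity: 4.10 / 200 = 0.0205 mSv/MBq.
- At 220 MBq: 220 x 0.0205 = 4.51 mSv PET, and 4.51 + 0.81 = 5.32 mSv per scan.
- +10% at one scan, 200 MBq at the other: 5.32 + 4.91 = 10.23 mSv.
- +10% at both: 2 x 5.32 = 10.64 mSv.
- Break-even PET dose: (10 - 2 x 0.81) / 2 = 4.19 mSv, which is 4.19 / 0.0205 = 204.4 MBq. With +10% at both scans this is a prescription of 204.4 / 1.10 = 185.8 MBq, or 92.9 kg.

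Two-scan totals with +10% at both scans, taking 4.10 mSv as the 200 MBq value:

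| Weight | Prescribed | Tolerance may exceed 200 MBq | 200 MBq is a hard cap |
|---|---|---|---|
| 90 kg | 180 MBq | 9.74 mSv | 9.74 mSv |
| 95 kg | 190 MBq | 10.19 mSv | 9.82 mSv |
| 100 kg | 200 MBq | 10.64 mSv | 9.82 mSv |

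**5. The alternative dosimetry reading.** If 4.10 mSv was computed at 220 MBq, the tolerance is already inside the table and 2 x (4.10 + 0.81) = 9.82 mSv is the true maximum even at +10% on both scans.

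**6. CT.** The table holds one low-dose CT per scan and section 12.5 lists one attenuation-correction CT; these fit each other. The synopsis adds the word diagnostic. The protocol gives no dose for a diagnostic CT, so no total can be computed. From step 3, any uncounted CT adding more than 0.09 mSv per scan takes two scans past 10 mSv, even with a hard cap at 200 MBq if the table is computed at that activity.

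**The case against.** The strongest reply is that the protocol attaches the maximum to the activity actually given. Section 11.1.1.6 speaks of administered activity, section 12.5 and the synopsis of what participants receive, and all three stop at 200 MBq. On that reading the tolerance works only beneath the cap and 9.82 mSv is correct. This is a fair literal reading. It does not remove the conflict, because the tolerance sentence then needs a qualification that it lacks for every prescription above about 182 MBq.

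A reader might infer that a patient treated fully within protocol will receive 10.64 mSv. The documents do not support that. The figure needs both assumptions in step 4 of the working, and also a patient at the top of the weight range with +10% at both scans, among at most six patients.

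A reader might also infer that a limit on patients is breached. Section 8 describes 10 mSv as a standard limit for healthy controls. Volunteers have one scan, at most 5.32 mSv even in the upper case, and section 8 sets no limit for patients. Nor is that comparison the reason for scanning patients twice: sections 7.3 and 12.5 give the dexamethasone comparison as the purpose. An exceedance would make the statement in section 8 wrong, and no more than that can be shown.

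Finally, it is tempting to say that a diagnostic CT would certainly break the 10 mSv figure. No dose for one is given, and the synopsis phrase may describe a single low-dose CT serving both purposes. The exclusion of contrast allergy in section 10.2 adds some doubt about which CT is planned, but does not establish that a further one is done.

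**Conclusion.** The point holds as an internal conflict with a conditional numerical consequence. Without any assumption, the maximum and the tolerance disagree above about 182 MBq (about 91 kg), the table headed as a maximum does not state its activity, and the synopsis and the detailed procedure differ on CT.

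The two-scan patient total is 9.82 mSv if 200 MBq is a hard cap or if 4.10 mSv was computed at 220 MBq. It can reach 10.23 to 10.64 mSv, at most 6.4% over 10 mSv, if 4.10 mSv is the 200 MBq value and the tolerance may exceed 200 MBq; with +10% at both scans it passes 10 mSv from about 93 kg. The effect of any separate diagnostic CT cannot be sized beyond the 0.09 mSv per scan margin.

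Confidence is moderate. The conflict deserves correction because it concerns a safety figure that the protocol relies on, but the documents do not show that the figure is wrong, so it ranks below an essential correction.

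**What to change.** Reconcile the synopsis (treatment period), section 8, section 11.1.1.6 and section 12.5 on three questions:

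1. whether the +/-10% tolerance may take administered activity above 200 MBq;
2. which activity underlies 4.10 mSv;
3. which CT acquisitions are performed at each visit and counted in the table.

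Then recompute the table for the largest activity and the CT acquisitions that the settled text permits, print the activity beside the dose, and make the stated maximum and the comparison with 10 mSv in section 8 agree with it. Which activity, tolerance or CT is right is for the sponsor and its radiation experts to decide; nothing here proposes one.

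The cost is a short recalculation and wording changes in an amendment. The downside is that the stated total may become slightly less favourable.
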